**Aims:** Given the proposed study is a pilot trial, the main purpose is to assess whether the intervention is feasible, and determine participants' acceptance of the program. Various markers of program feasibility and acceptability will be assessed, such as (a) university students' interest in the program, and feasibility of recruitment, (b) participant satisfaction with virtual running groups, (c) affective attitudes towards exercising, (d) participant adherence to the program and control condition, (e) participation rates of group activities, (f) completion rates of assessments, and (g) participants' perception of whether a virtual running group provided adequate social connection.

Although formal hypothesis testing of efficacy is ill-advised in pilot studies given their lack of power (Eldridge et al., 2016), we will examine secondary outcomes that have theoretical and practical importance for exploratory purposes, and calculate statistical information such as effect sizes and measurement variance for informing power analyses when planning future efficacy trials. The secondary outcomes include changes in perception of social support in the context of exercise, global well-being (i.e., flourishing), exercise related well-being (i.e., subjective vitality), exercise identity, and exercise behaviour. Participants' ratings of social identification with their running group will also be assessed at the end of the program (Week 8).

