**Research Design:** The study will utilize a two-arm, parallel group, unblinded randomized controlled pilot trial design. UBC undergraduate students ( $N = 60$ ) will be equally randomized to either an eight-week social identity building virtual running group ( $n = 30$ ) or an eight-week control group ( $n = 30$ ). The group component of the intervention will be delivered via Zoom to support social connection among running group members and the fitness/social media app Strava so participants can post their runs and walks for members of their running group to view and provide words of encouragement. The virtual component is utilized to adhere to physical distancing protocols associated with the current COVID-19 pandemic. The attention control group will receive information regarding physical activity guidelines, be encouraged to meet the Canadian physical activity guidelines, and be asked to record their runs and walks on Strava. The use of an attention control condition will enable us to control for any potential effect of tracking exercise on outcomes such as well-being, exercise identity, and exercise behaviour.

**Study Population:** The target population are UBC undergraduate students (18+ years and enrolled in part time or full time studies) that have been underactive (i.e., not meeting the Canadian guidelines of 150 minutes of moderate-to-vigorous exercise per week) in the past month. Participants must be able to speak and read English, be living in Canada, and not experience any health contraindication that might prevent that person from participating in moderate-to-vigorous intensity exercise. Participants must own a smartphone so they can record their runs and walks on Strava, and have access to the internet and own a device that has camera functionality (e.g., computer) for attending the virtual coffee chats hosted on Zoom.

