group they are in by phone and email. Participants in the intervention condition will be directed to the UBC Canvas portfolio and asked to attend the first meet-and-greet meeting facilitated by the student investigator. During the meet-and-greet, participants will be (a) introduced to the Canvas materials that facilitate their participation in the running group, (b) provided instruction for Strava use, (c) provided information about the group goal, (d) provided explanation of the weekly structure of the program, (e) provided running and exercise considerations (hydration, nutrition, warm-up, safety, footwear and clothing, running pacing), as well as instructed to inform their physician if they experience negative symptoms when exercising (e.g., difficulty breathing) (f) asked to introduce themselves to their running group and brainstorm a team name. The Canvas website will include (a) information about the study (e.g., group goal explanation, Strava instructions), (b) a weekly video providing tips on running (from YouTube), (c) a videoconferencing link for the weekly coffee chats, and (d) discussion questions for the weekly coffee chat. The student investigator will coordinate the completion of the baseline and post-intervention surveys, as well as weekly exercise logs.

We will use a rolling recruitment strategy. As soon as the first 12 participants are recruited, they will be randomized to the virtual running group program or the control group, and begin participation (i.e., cohort 1). If more than 12 participants are recruited (e.g., 24 participants), then 2 cohorts will be created and will begin participating at the same time. Therefore, multiple cohorts will likely begin participation in the study at different time points. We will aim for five cohorts in total (N = 60).

**Randomization:** Once participants complete the baseline questionnaire, they will be randomized to the intervention group (n = 30) or the control group (n = 30) using a random number generator. We aim for 50% recruitment of men and 50% recruitment of women. We will stratify to ensure equal distribution of men and women across conditions. Sequence generation will be completed separately for men and women using the randomizer.org tool for researchers, with blocks of 2 unique numbers (1, 2) with each number designating one of the two randomization groups. Participants will be randomized in the order they complete the baseline survey.

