## **Data Collection**

Participants will be asked to complete baseline measures on Qualtrics before they are randomized to the intervention or control group, which will include demographics (e.g., age, gender, academic year in university), affective attitudes towards exercising, social support,

flourishing, exercise-related subjective vitality, exercise identity, and exercise behaviour. Participants will be provided 10 dollars for completing the baseline questionnaire. Each week, participants will be sent an email to record their exercise in the following week. They will be asked to log the type of exercise and the duration of the activity. At the end of the study (Week 8), participants will be asked to complete an online post-intervention assessment, via Qualtrics, of satisfaction with the program (intervention group only), affective attitudes towards exercising, social support, flourishing, exercise-related subjective vitality, exercise identity, social identification with the running group (intervention group only), and exercise behaviour. Participants will also be provided 10 dollars for completing the post-intervention questionnaire. Finally, 10 participants in the intervention group will be chosen at random to complete semi-structured interviews assessing the feasibility and acceptability of the intervention. Participants will be offered 20 dollars for completing the interview.

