### **Exercise Behaviour**

Participant will report their moderate-to-vigorous exercise minutes per week (over the past month) using a modified version of the Godin leisure time exercise questionnaire (Courneya et al., 2004; Godin & Shephard, 1985).

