### **Analysis Plan**

With respect to the primary feasibility and acceptability outcomes, frequency values will be calculated for adherence to the program, number of weekly physical activity logs completed, number of Zoom group meetings attended, and number of post-intervention surveys completed. Descriptive statistics (mean, variance), skewness, and kurtosis will be calculated for the affective attitude items and the one item assessing program satisfaction. Cronbach’s alpha will be calculated for the four affective attitude items. A 2 x 2 within and between subjects ANOVA will be conducted to examine intervention by time effects on affective attitudes towards exercise. Effect sizes ( $\eta^2$ ) will also be calculated for the between, within, and interaction effects.

The interviews with participants will be transcribed verbatim. The transcripts will be analyzed using thematic analysis. First, codes will be generated to identify content that is relevant to understanding participants’ experiences with the program and virtual running crew/group. Second, codes will be analyzed to produce higher order themes regarding participants’ experiences with the program and virtual running crew/group (Clarke & Braun, 2017).

With respect to exploratory analyses, descriptive statistics (mean, variance), skewness, kurtosis, and Cronbach's alpha will be calculated for each secondary outcome variable. Multiple 2 x 2 within and between subjects ANOVAs will be conducted to examine intervention by time effects on perceived social support, flourishing, exercise-related subjective vitality, exercise identity, and exercise behaviour. Effect sizes ( $\eta^2$ ) will also be calculated for the between, within, and interaction effects.

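### The intervention effect is estimated only by arm-by-time ANOVA terms with eta-squared; a baseline-adjusted Week 8 difference with a 95% CI would serve the stated planning aim better

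*Combined protocol and SAP*

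**What the plan says.** The Analysis Plan section gives the same model to six outcomes. For affective attitudes, listed among the primary feasibility and acceptability outcomes, "A 2 x 2 within and between subjects ANOVA will be conducted to examine intervention by time effects on affective attitudes towards exercise". For perceived social support, flourishing, subjective vitality, exercise identity and exercise behaviour, "Multiple 2 x 2 within and between subjects ANOVAs will be conducted to examine intervention by time effects". In both cases eta-squared values "will also be calculated for the between, within, and interaction effects". Means, variances, skewness, kurtosis and Cronbach's alpha are also planned, without saying that they will be given by arm and time point.

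The Aims section advises against formal efficacy testing in a pilot and gives the purpose of these statistics: to "calculate statistical information such as effect sizes and measurement variance for informing power analyses when planning future efficacy trials".

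The material for an adjusted analysis is already there. Under Data Collection, "Participants will be asked to complete baseline measures on Qualtrics before they are randomized to the intervention or control group", and every outcome in the ANOVAs is measured then and again at Week 8. Under Randomization, "We will stratify to ensure equal distribution of men and women across conditions".

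Nowhere does the document plan a between-arm difference in scale units, a confidence interval, a pre-post correlation or a baseline-adjusted model.

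**The concern.** The planned summary does not match its stated use. Someone sizing the larger trial needs a signed difference with its uncertainty, the SD, and the pre-post correlation if that trial is to be analysed with baseline adjustment. Eta-squared for the interaction has no sign and mixes the size of the effect with the pre-post correlation. The plan does not say whether the classical or the partial form is meant, and the two differ several-fold for the same effect. The main effect of arm does not help, because it averages baseline and Week 8 and so carries only half of a Week 8 difference.

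The change-score contrast behind the interaction is also less precise than a baseline-adjusted comparison when the SDs at the two times are similar. Without an interval, a reader could take one effect size from 60 people as a firm planning value.

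**Working it through.** **Inputs from the document.** 30 per arm (Research Design; Randomization); one baseline and one Week 8 measurement (Data Collection); running groups of six in the intervention arm (Virtual Running Group Condition). The plan gives no SD, correlation, alpha or target difference, so it has no figure to reproduce.

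**Assumed inputs.** Week 8 SD = 1; baseline SD = k (1, 0.75 or 0.5); pre-post correlation r = 0.3 / 0.5 / 0.7; multiplier 1.96.

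**Step 1: what the interaction tests.** With two time points, the arm-by-time F equals the squared t statistic on change scores. On one simulated data set both were 4.2208.

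**Step 2: precision.**
- Change contrast: half-width = 1.96 × √[(k² + 1 − 2rk) × 2/30].
- Baseline-adjusted: half-width = 1.96 × √[(1 − r²) × 2/30], for any k.
- The two variance factors differ by (k² + 1 − 2rk) − (1 − r²) = (k − r)². In large samples adjustment is therefore never less precise, and the gain is nil when k = r.

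| Baseline SD (k) | Change, r = 0.3 / 0.5 / 0.7 | Adjusted | Variance ratio, adjusted to change |
|---|---|---|---|
| 1 | 0.60 / 0.51 / 0.39 | 0.48 / 0.44 / 0.36 | 0.65 / 0.75 / 0.85 |
| 0.75 | 0.53 / 0.46 / 0.36 | 0.48 / 0.44 / 0.36 | 0.82 / 0.92 / 1.00 |
| 0.5 | 0.49 / 0.44 / 0.37 | 0.48 / 0.44 / 0.36 | 0.96 / 1.00 / 0.93 |

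A small-sample factor of 1 + 1/56 moves the last row's ratios to 0.975 / 1.018 / 0.944, so the worst loss is about 2% in variance. A simulation of 20,000 runs, regressing on arm, baseline and gender (gender given no effect), agreed. At k = 1 the half-widths were 0.596 / 0.505 / 0.393 for change and 0.489 / 0.441 / 0.364 adjusted.

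A small k is plausible for exercise minutes. Study Population admits only students "not meeting the Canadian guidelines of 150 minutes of moderate-to-vigorous exercise per week" in the past month, and the exercise outcome asks about the same behaviour over the same look-back period.

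**Step 3: dropout and clustering.**
- With 24 per arm (assumed 20% dropout) and k = 1: 0.67 / 0.57 / 0.44 for change, 0.54 / 0.49 / 0.40 adjusted.
- With clustering in the intervention arm only, the adjusted half-width at r = 0.5 is 1.96 × √[0.75 × (1 + 1 + 5 × ICC)/30]. This gives 0.44 at ICC 0, 0.46 at 0.05 and 0.49 at 0.10.

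**Step 4: why eta-squared is hard to plan from.** For equal arms and k = 1, partial eta-squared = f²/(1 + f²), where f² = d²/[8(1 − r)].
- A true d of 0.5 gives 0.043, 0.059, 0.094 or 0.135 at r = 0.3, 0.5, 0.7 or 0.8.
- In reverse, a partial eta-squared of 0.06 corresponds to d = 0.60, 0.51, 0.39 or 0.32.
- Classical eta-squared for d = 0.5, with no change in controls, takes interaction, arm and time sums of squares of 2 × 60 × (0.5/4)² = 1.875 each and a residual of 120. It is 1.875/125.625 = 0.015.

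**Step 5: planning range.** Suppose an observed difference of 0.5 SD at r = 0.5 and k = 1, with the next trial at 80% power and two-sided 5%.
- Change: −0.01 to 1.01, or 17 per arm to no effect (64 at the point estimate).
- Adjusted: 0.06 to 0.94, or 15 to about 3,100 per arm (49 at the point estimate).

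**The case against.** The strongest reply is that this is a preference between two valid analyses in a pilot whose main purpose is feasibility. The arm-by-time term is unbiased under randomisation, and no feasibility conclusion depends on it. That stands and limits the weight of the point. But the exploratory analyses have a stated purpose, and the summary should fit it.

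A second reply is that the missing quantities could be derived. Given cell means and variances and the partial eta-squared, a reader can work back to the signed difference, its standard error, the pooled pre-post correlation and the adjusted difference. This is correct, but it requires summaries by arm and time and a named form of eta-squared, and the plan commits to neither.

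Third, if the larger trial keeps the same arm-by-time test, partial eta-squared converts directly into its power input. That is true, but the direction and the uncertainty would still be missing.

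Fourth, the precision gain rests on assumed correlations and SDs and may be nil for exercise minutes. That is accepted. The missing interval and the poor portability of eta-squared do not depend on those values.

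Fifth, the planning range is fragile. With t quantiles the adjusted upper bound becomes about 4,300 per arm. With 24 per arm, or with an ICC of 0.10, the adjusted lower limit falls just below zero. The range should therefore be read as showing that both analyses are imprecise, not as a case for adjustment.

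Lastly, no gain from the gender covariate has been shown. It is proposed because gender is the stratification factor.

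**Conclusion.** The point holds as a worthwhile improvement at low cost. The planned analysis is valid, but its effect summary is unsigned, has no interval, and cannot be converted to a difference without a correlation that the plan does not undertake to report.

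The gain in precision depends on inputs the document does not give. With equal SDs and correlations of 0.3 to 0.7, the variance falls by 35% to 15%. With a baseline SD half that at Week 8, the change ranges from a 7% reduction to none, or about 2% more variance in the worst small-sample case. Apart from the separate dropout and ICC illustrations, these figures assume no dropout and no clustering.

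**What to change.** For affective attitudes and the five secondary outcomes, make the main exploratory estimate the Week 8 mean difference (intervention minus control), adjusted for the baseline score and gender, with its 95% CI. Alongside it, report:

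- the mean and SD by arm and time point;
- the pre-post correlation;
- how the interval widens under an assumed running-group ICC, for example 0.05 and 0.10, since five groups of six are too few to estimate an ICC well.

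If the ANOVAs and eta-squared stay, call them descriptive and name the form of eta-squared. State that the pilot estimate alone should not size the next trial.

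The cost is one regression per outcome and some wording, with no new data. For an outcome whose baseline SD is much smaller than its Week 8 SD, there may be little or no gain in precision.
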